	and most frequent in our daily clinical practice) depending on the
	molecular subgroup.
	We therefore propose a study to evaluate the rate of lymph node
	involvement depending on the molecular subgroup in early-stage EC
	(I/II).
Study design:	International, retrospective, multicentre, observational study.
Sites number:	Not defined
Objectives:	Primary objective
	-To evaluate the lymph node involvement rate (sentinel) for each
	molecular subtype in patients with stage I/II EC
	Secondary objectives
	-To evaluate the lymph node involvement rate (sentinel and non-
	sentinel) for each prognostic risk group in patients with stage I/II EC
	-To evaluate morbidity associated to SLN biopsy
	, , ,
	-To assess compliance of ESGO quality Indicators
Study population:	
Study population:	-To assess compliance of ESGO quality Indicators
Study population:	-To assess compliance of ESGO quality Indicators Patients with early-stage (FIGO stage I-II) EC that underwent surgical
Study population:	-To assess compliance of ESGO quality Indicators Patients with early-stage (FIGO stage I-II) EC that underwent surgical treatment with lymph node evaluation between January 2021 to
Study population:	-To assess compliance of ESGO quality Indicators Patients with early-stage (FIGO stage I-II) EC that underwent surgical treatment with lymph node evaluation between January 2021 to
Study population:	-To assess compliance of ESGO quality Indicators Patients with early-stage (FIGO stage I-II) EC that underwent surgical treatment with lymph node evaluation between January 2021 to December 2022, both included.
Study population:	-To assess compliance of ESGO quality Indicators Patients with early-stage (FIGO stage I-II) EC that underwent surgical treatment with lymph node evaluation between January 2021 to December 2022, both included. A sample size of 1,032 patients may provide sufficient statistical
Study population:	-To assess compliance of ESGO quality Indicators Patients with early-stage (FIGO stage I-II) EC that underwent surgical treatment with lymph node evaluation between January 2021 to December 2022, both included. A sample size of 1,032 patients may provide sufficient statistical power to evaluate the association between molecular subgroups
Study population:	-To assess compliance of ESGO quality Indicators Patients with early-stage (FIGO stage I-II) EC that underwent surgical treatment with lymph node evaluation between January 2021 to December 2022, both included. A sample size of 1,032 patients may provide sufficient statistical power to evaluate the association between molecular subgroups and lymph node status. We assumed a 90% power for a 2-sided p-
Study population:	-To assess compliance of ESGO quality Indicators Patients with early-stage (FIGO stage I-II) EC that underwent surgical treatment with lymph node evaluation between January 2021 to December 2022, both included. A sample size of 1,032 patients may provide sufficient statistical power to evaluate the association between molecular subgroups and lymph node status. We assumed a 90% power for a 2-sided p-value of 0.05 and a minimum difference of 4.4 percentage points in

Inclusion criteria:	-Age 18 years or older		
	-Patient was operated during 2021-2022		
	-Histological confirmation of Endometrial Cancer with endometrioid		
	histology or high risk histology (serous, clear cell, carcinosarcoma		
	and mixed histologies)		
	-Preoperative FIGO stage I or II by MRI or US		
	-Preoperative CT-Scan or PET-CT without evidence of local or distant		
	disease (could be omitted in low-risk and intermediate		
	endometrial carcinoma with low grade histology)		
	-Surgical protocol according to ESGO/ESTRO/ESP guidelines		
	-A detailed sentinel lymph node study protocol must be accredite		
	either by ultra-staging or OSNA		
	-Molecular analysis performed on the pathology specimen		
	according to ESGO/ESTRO/ESP guidelines (POLE mutation analysis		
	could be omitted in low-risk and intermediate risk endometrial		
	carcinoma with low grade histology).		
Exclusion criteria:	-Pregnant women		
	-Previous hysterectomy		
	-Previous pelvic/para-aortic lymphadenectomy		
	-Presence of extra-uterine disease (peritoneal, visceral or suspicious		
	lymph node metastasis)		
	-Past medical history of any invasive tumor		
	-History of previous abdominal or pelvic radiotherapy of any type		
	(including braquitherapy)		
	-History of preoperative neoadjuvant chemotherapy		
Statistical	Quantitative data will be presented as mean and standard deviation		
considerations:	and qualitative variables with absolute values and percentages.		
	Additionally, qualitative variables among groups will be compared		
	by chi-square test or Fisher exact test; and quantitative variables		

with t-test and ANOVA test. For the multivariate analysis a logistic regression model will be used. Alpha error will be set at 5%

3. BACKGROUND

The management of endometrial cancer (EC) is currently undergoing a true revolution in terms of diagnosis and treatment. Since 2013 and thanks to the TCGA project¹ (The Cancer Genome Atlas), four distinct molecular subgroups (POLE, MMR-D, Copy number low, Copy number high) with distinct prognostic implications were identified.

Subsequently, PROMISE study² brought this "new era" closer to daily clinical practice. These new findings led ESGO³ (European Society of Gynecologic Oncology) to decide to integrate this molecular classification into the definition of the different risk groups.

Currently, thanks to the retrospective analysis of the PORTEC-3 cohort^{4,5}, we know that these four molecular subgroups may present differences in survival in high-risk patients depending on the type of treatment proposed, chemoradiotherapy vs. adjuvant radiotherapy. This question will be answered by the RAINBO trial⁶ (Refining Adjuvant treatment IN endometrial cancer Based On molecular profile).

On the other hand, the surgical management of early endometrial cancer (stage I/II) has been changing for some years now, especially with regard to nodal staging, from modulation of treatment depending on the risk group (pelvic lymphadenectomy +/-sentinel lymph node (SLN) for low and intermediate risk groups vs. aortopelvic lymphadenectomy +/- SLN for those at high risk) to a generalization of treatment based on detailed study of the sentinel node following the algorithm described by the group of Abu-Rustum NR et al⁷.

Just as the RAINBO study will try to clarify the type of adjuvant treatment necessary for each molecular subgroup, we do not currently know if it could be possible to tailor the type of lymph node staging in early EC (the most common and most frequent in our daily clinical practice) depending on the molecular subgroup^{8,9}.

We therefore propose a study to evaluate the lymph node involvement rate depending on the molecular subgroup in early-stage EC (I/II).

4. OBJECTIVES

Primary objective

-To evaluate the lymph node involvement rate (sentinel) for each molecular subtype in patients with stage I/II EC.

Secondary objectives

- -To evaluate the lymph node involvement rate (sentinel and non-sentinel) for each prognostic risk group in patients with stage I/II EC.
- -To evaluate morbidity associated to SLN biopsy.
- -To assess compliance of ESGO quality Indicators.

We consider that our study will help to:

- ✓ Tailor the type of nodal staging depending on the molecular subgroup in early EC.
- ✓ Take a snapshot of the morbidity in SLN.
- ✓ Evaluate if the quality indicators described by ESGO are met.
- ✓ Know the degree of correlation between the molecular classification of the preoperative and the definitive biopsy.

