5. STUDY GENERAL DESIGN

STUDY GENERAL DESIGN

The study is a retrospective multicentric international observational study reviewing data of patients diagnosed with early-stage (FIGO stage I-II) EC and underwent surgical treatment with lymph node evaluation between January 2021 to December 2022, both included.

All data and records generated during this study will be kept confidential in accordance with Institutional policies and HIPAA on subject privacy. The Investigators and other site personnel will not use such data and records for any purpose other than conducting the study.

This protocol will be reviewed by the IRB of Clinica Universidad de Navarra, and the data collection will not start until the IRB approval is obtained. Each institution will be responsible of obtaining its own IRB/EC approval.

RECRUITMENT

A sample size of 1,032 patients may provide sufficient statistical power to evaluate the association between molecular subgroups and lymph node status. We assumed a 90% power for a 2-sided p-value of 0.05 and a minimum difference of 4.4 percentage points in prevalence rates of positive lymph nodes. We anticipated a potential dropout rate of 10%.

Gynaecological Cancer Centres/Units and hospitals regularly performing elective surgeries for EC internationally will be invited to participate in this study. Invitations will be sent through international/national and informal networks. Participating sites will register with the central audit team at Clinica Universidad de Navarra and will be provided with unique user access credentials for the database.

Each participating site (centre/unit/trust/hospital) will identify a principal investigator (PI) who will be responsible for coordinating data entry at their local site. The PI may have a bigger local reporting group/team with as many individuals as felt to be necessary to sustain the project. Team members may include gynaecological oncology trainees/fellows, medical/clinical oncologists, radiologists, pathologists, nurses, medical students, research staff, data managers. Each participating site will be provided a unique site code, individual username and password for database access. Inputting sites will only be able to access/see their own data and will not be able to see another site's data. The central coordinating centre team will be able to see individual data from all sites.

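### Does the plan need a named analysis of sentinel plus non-sentinel involvement by molecular subtype?

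*Combined protocol and SAP*

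**What the plan says.** Section 4 (Objectives) has two nodal objectives. The primary is "To evaluate the lymph node involvement rate (sentinel) for each molecular subtype in patients with stage I/II EC". The first secondary is "To evaluate the lymph node involvement rate (sentinel and non-sentinel) for each prognostic risk group in patients with stage I/II EC". The synopsis lists the same pair. The other secondary objectives concern morbidity of sentinel biopsy and the ESGO quality indicators. The same section hopes the study will help to "Tailor the type of nodal staging depending on the molecular subgroup in early EC".

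Other places use wider wording. Section 3 (Background) ends with "We therefore propose a study to evaluate the lymph node involvement rate depending on the molecular subgroup in early-stage EC". Section 5 (Recruitment) sizes the study at 1,032 patients to "evaluate the association between molecular subgroups and lymph node status", with 90% power, a two-sided 0.05 level, 10% dropout and a "minimum difference of 4.4 percentage points in prevalence rates of positive lymph nodes". Neither place says sentinel.

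Section 6 makes a detailed sentinel node protocol (ultrastaging or OSNA) a condition of entry. Section 7 sorts patients into POLEmut, MMRd, NSMP and p53abn. Section 8 compares qualitative variables among groups by chi-square or Fisher exact test and adds a logistic regression. It names no outcome.

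**The concern.** Section 4 separates the two node definitions, so a reader may expect the unqualified wording in sections 3 and 5 to mean any positive node. On that reading the study would be sized for an outcome that no objective reports by molecular subtype.

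The point also touches the intended use. Among patients with a sentinel node examined, the sentinel rate can only equal or fall below the any-node rate. Someone deciding how to stage nodes by subtype would want to know how many patients in each subtype were positive only outside the sentinel node. If no analysis is named, that count might be left out or chosen after the data are seen. The denominator of the sentinel rate is also unstated, including how patients with failed mapping count.

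**Working it through.** **1. Which node definition does the sample size use?**

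Inputs from section 5: N = 1,032, 10% dropout, 4.4 points, 90% power, two-sided 0.05. The documents give neither a base rate nor group shares, so both are assumed here.

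Evaluable patients: 1,032 × 0.90 = 928.8, about 929.

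For two equal groups with pooled variance, n per group = {[1.96 √(2p̄(1−p̄)) + 1.2816 √(p₁(1−p₁) + p₂(1−p₂))] / (p₂−p₁)}².

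| Assumed rates | n per group | Total evaluable |
|---|---|---|
| 2.3% vs 6.7% | 465 | 930 |
| 5.0% vs 9.4% | 724 | 1,448 |
| 10.0% vs 14.4% | 1,161 | 2,322 |

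For the first row: (1.96 × 0.2932 + 1.2816 × 0.2915) / 0.044 = 21.55, and 21.55² = 464.4. So 2.3% vs 6.7% matches the stated N, but other unstated combinations do too, for example 1.7% vs 6.1% at 2:1 (939 evaluable). The arithmetic cannot show whether the rates are sentinel or any-node. The text has to settle it.

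**2. The passages side by side.**

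| Place | Nodes | Grouping |
|---|---|---|
| Section 4, primary | sentinel | molecular subtype |
| Section 4, first secondary | sentinel and non-sentinel | risk group |
| Section 3, aim | not qualified | molecular subgroup |
| Section 5, sample size | not qualified | molecular subgroup |

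The last two rows share their grouping with the primary objective and with no other. The Background also describes the move to staging based on the sentinel node shortly before it states the aim. Shorthand for sentinel status is the natural reading.

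**3. What if any-node status was meant?**

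Let f be the share of node-positive patients who are positive only outside the sentinel node. All values of f are assumptions.

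*Same f in every subtype.* The sentinel difference is 4.4 × (1 − f): 4.31, 4.18 and 3.96 points for f = 2%, 5% and 10%. Power is Φ{[(p₂−p₁)√n − 1.96 √(2p̄(1−p̄))] / √(p₁(1−p₁) + p₂(1−p₂))}, with both rates multiplied by (1 − f).

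| Start | f = 2% | f = 5% | f = 10% |
|---|---|---|---|
| 2.3% vs 6.7%, n = 465 | 89.4% | 88.4% | 86.6% |
| 5.0% vs 9.4%, n = 724 | 89.4% | 88.4% | 86.5% |
| 10.0% vs 14.4%, n = 1,161 | 89.3% | 88.3% | 86.3% |

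*f = 10% in one subtype and zero in the other.*

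- 2.3% vs 6.7%: 6.7 × 0.9 − 2.3 = 3.73, or 6.7 − 2.3 × 0.9 = 4.63 points.
- 5.0% vs 9.4%: 9.4 × 0.9 − 5.0 = 3.46, or 9.4 − 5.0 × 0.9 = 4.90 points.
- 10.0% vs 14.4%: 14.4 × 0.9 − 10.0 = 2.96, or 14.4 − 10.0 × 0.9 = 5.40 points.

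At 1:1 only the first pair fits 929 evaluable patients. The other two need 1,448 and 2,322, so the wider range of 3.0 to 5.4 points illustrates a different study. Nothing in the documents supports a gap confined to one subtype.

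**4. What would the extra table show?**

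Assume subtypes of 5%, 10% and 25% of 929, that is 46, 93 and 232 patients, with any-node rates near 10%. Wilson 95% intervals are 4.7–23.0% (5/46), 5.2–17.4% (9/93) and 6.7–14.4% (23/232). Splitting by lymphadenectomy widens them: if the 46 divide evenly, 2/23 gives about 2–27%. In patients without lymphadenectomy the any-node rate is essentially the sentinel rate again.

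**The case for a change.** The best case for a change is that permission is not prespecification. Section 8 would allow the any-node comparison without asking for it. A rate by risk group is not a rate for POLEmut or p53abn, even though the Background says ESGO chose to "integrate this molecular classification into the definition of the different risk groups". The count of sentinel-negative, non-sentinel-positive patients bears directly on tailoring nodal staging, and it needs no new data because the first secondary objective already requires non-sentinel status.

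The textual part stands: no objective names this table, section 5 does not say which nodes it means, and the sentinel denominator is not written down. The inference to a defect does not. The table would be supportive and untested, so choosing it late does little harm. Non-sentinel nodes are seen only where they were removed, and the plan asks for ultrastaging or OSNA of sentinel nodes only. Removal may follow risk group and therefore molecular class, and splitting by lymphadenectomy does not remove that selection. Leaving such a table out of the named objectives is a fair choice.

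The denominator is a reporting matter that an analyst will meet at once: the rate cannot be printed without a count beneath it, and failed mapping can be reported beside it. Limiting it to patients with a sentinel node examined would be a substantive choice about failed mapping, not a neutral clarification.

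**Conclusion.** The concern does not call for a change. The primary outcome is explicit, defensible and tied to the nodes examined by a detailed protocol. The unqualified wording in sections 3 and 5 most naturally refers to it, and the missing details are ones analysts fill in the ordinary course of reporting.

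If any-node status had been meant, a gap common to all subtypes would cost little: 90% power falls to between 86% and 87% at an assumed f of 10%. With rates that fit the stated N at 1:1 (2.3% vs 6.7%, also assumed), a 10% gap in one subtype alone moves the difference from 4.4 to about 3.7 or 4.6 points. The documents give no value of f by subtype, so its true size cannot be derived.

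This judgement rests on reading section 5 as sentinel status. It does not settle whether 1,032 is adequate for four subtypes, which is a separate question.

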5. STUDY GENERAL DESIGN

STUDY GENERAL DESIGN

The study is a retrospective multicentric international observational study reviewing data of patients diagnosed with early-stage (FIGO stage I-II) EC and underwent surgical treatment with lymph node evaluation between January 2021 to December 2022, both included.

All data and records generated during this study will be kept confidential in accordance with Institutional policies and HIPAA on subject privacy. The Investigators and other site personnel will not use such data and records for any purpose other than conducting the study.

This protocol will be reviewed by the IRB of Clinica Universidad de Navarra, and the data collection will not start until the IRB approval is obtained. Each institution will be responsible of obtaining its own IRB/EC approval.

RECRUITMENT

A sample size of 1,032 patients may provide sufficient statistical power to evaluate the association between molecular subgroups and lymph node status. We assumed a 90% power for a 2-sided p-value of 0.05 and a minimum difference of 4.4 percentage points in prevalence rates of positive lymph nodes. We anticipated a potential dropout rate of 10%.

Gynaecological Cancer Centres/Units and hospitals regularly performing elective surgeries for EC internationally will be invited to participate in this study. Invitations will be sent through international/national and informal networks. Participating sites will register with the central audit team at Clinica Universidad de Navarra and will be provided with unique user access credentials for the database.

Each participating site (centre/unit/trust/hospital) will identify a principal investigator (PI) who will be responsible for coordinating data entry at their local site. The PI may have a bigger local reporting group/team with as many individuals as felt to be necessary to sustain the project. Team members may include gynaecological oncology trainees/fellows, medical/clinical oncologists, radiologists, pathologists, nurses, medical students, research staff, data managers. Each participating site will be provided a unique site code, individual username and password for database access. Inputting sites will only be able to access/see their own data and will not be able to see another site's data. The central coordinating centre team will be able to see individual data from all sites.

Study IDs are unique to each patient and will be automatically assigned when a patient is registered onto the database. Study IDs will be assigned centrally by the REDCap bespoke database. Only one study ID should be created for each patient and new data registered on the appropriate electronic case record file (eCRF). Individual centres will retain access to their patient data and not provide identifiable information on the international database. Local sites will retain information on patient identifiable data (name, date of birth, address, telephone number) in a separate file but not share this with the central audit team. This information/file that links the study ID to the patient identifiers will be kept on the local centre/unit/hospital server, in case further clarification of data is required.

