6. STUDY POPULATION

INCLUSION CRITERIA

A patient will be considered eligible for inclusion in this study if all the following criteria are met:

- -Age 18 years or older
- -Patient was operated during 2021-2022
- -Histological confirmation of Endometrial Cancer with endometrioid histology or high risk histology (serous, clear cell, carcinosarcoma and mixed histologies)
- -Preoperative FIGO stage I or II by MRI or US
- -Preoperative CT-Scan or PET-CT without evidence of local or distant disease (could be omitted in low-risk and intermediate risk endometrial carcinoma with low grade histology)
- -Surgical protocol according to ESGO/ESTRO/ESP guidelines
- -A detailed sentinel lymph node study protocol must be accredited, either by ultrastaging or OSNA
- -Molecular analysis performed on the pathology specimen according to ESGO/ESTRO/ESP guidelines (POLE mutation analysis could be omitted in low-risk and intermediate risk endometrial carcinoma with low grade histology).

EXCLUSION CRITERIA

-Pregnant women

-Previous hysterectomy

-Previous pelvic/para-aortic lymphadenectomy

-Presence of extra-uterine disease (peritoneal, visceral or suspicious lymph node

metastasis)

-Past medical history of any invasive tumor

-History of previous abdominal or pelvic radiotherapy of any type (including

braquitherapy)

-History of preoperative neoadjuvant chemotherapy

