7. EVALUATION

Definition of variables

Sentinel lymph node: Defined as the first echelon lymph node where the tumor directly

flows through the lymphatic duct.

Isolated tumor cells: <0.2mm or less than 200 tumoral cells in a single histologic section

Micrometastases: 0.2mm-0.2cm or more than 200 tumoral cells in a single histologic

section.

Macrometastases: Metastases >0.2cm

Data to be abstracted:

Medical history and demographic data will be reviewed. Patients will be grouped in

group 1 (POLEmut), group 2 (MMRd), group 3 (NSMP), group 4 (p53abn), depending on

the molecular profile. Preoperative FIGO stage, modality of initial treatment, final

pathology diagnosis, preoperative pathology analysis, type of surgery, perioperative

details and adverse events will be reviewed. Follow up until the date will be reviewed as

well. (Appendix).

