8. STATISTICAL ANALYSIS

Quantitative data will be presented as mean and standard deviation and qualitative

variables with absolute values and percentages. Additionally, qualitative variables

among groups will be compared by chi-square test or Fisher exact test; and quantitative

variables with t-test and ANOVA test. For the multivariate analysis a logistic regression model will be used.

Survival analysis will be performed using the Kaplan-Meier method and log-rank tests. Alpha error will be set at 5%.

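### Patients may enter without a POLE result, but the plan has no rule for placing them in its four molecular groups, so the primary subtype comparison can be biased and its 90% power is not assured

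*Combined protocol and SAP*

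**What the plan says.** The primary objective in section 4 is "To evaluate the lymph node involvement rate (sentinel) for each molecular subtype in patients with stage I/II EC". The same section hopes the results will help to "Tailor the type of nodal staging depending on the molecular subgroup in early EC".

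Section 5 (Recruitment) gives the sample size: "A sample size of 1,032 patients may provide sufficient statistical power to evaluate the association between molecular subgroups and lymph node status". The inputs are "We assumed a 90% power for a 2-sided p-value of 0.05 and a minimum difference of 4.4 percentage points in prevalence rates", followed by "We anticipated a potential dropout rate of 10" percent. It does not name the contrast, the lower node rate or the subgroup shares. Nor does it say what the 10% covers, or whether 1,032 is before or after it.

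The inclusion criteria in section 6 require molecular analysis, with an exception: "POLE mutation analysis could be omitted in low-risk and intermediate risk endometrial carcinoma with low grade histology". Section 7 sorts patients into "group 1 (POLEmut), group 2 (MMRd), group 3 (NSMP), group 4 (p53abn), depending on" their molecular profile. Section 8 says that qualitative variables "among groups will be compared by chi-square test or Fisher exact test", and plans a logistic model without naming covariates.

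No section provides a category for unknown POLE status, a placement rule, a missing-data method or a sensitivity analysis for these patients.

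**The concern.** A patient without a POLE result can be neither called POLEmut nor confirmed as not POLEmut. Such patients are eligible and count towards 1,032, yet the plan does not say where they go. There are two routes.

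- **Placed by the other markers.** Untested POLEmut tumours are counted in another group, mainly NSMP, and the POLEmut group holds tested patients only. The test may be skipped only in lower-risk, low-grade disease, so POLEmut then over-represents higher-risk patients. A POLEmut–NSMP difference can reflect who was tested rather than tumour biology. A larger sample does not remove this.
- **Left out.** Fewer patients are compared than planned, and those who remain are a higher-risk selection.

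The primary result is the node rate per subtype, and it is meant to inform nodal staging by subtype. If the route is chosen after the data are seen, the choice itself could alter the conclusion.

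**Working it through.** **The plan's own figure.** With two equal groups and rates p1 and p2 = p1 + 0.044, where p̄ is their mean:

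n per group = [1.960·√(2p̄(1−p̄)) + 1.282·√(p1(1−p1) + p2(1−p2))]² / 0.044²

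1,032 in total (516 each) fits about 2.8% v 7.2%. If 1,032 already includes the 10% loss (1,032 × 0.9 = 928.8, so 928, or 464 each), it fits about 2.3% v 6.7%. Neither pair is in the documents, so the 90% can be neither confirmed nor refuted. Below it is taken as given.

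**Route 1: placed by the other markers.** Let v be the fraction of each subtype untested, g the node rate in tested minus untested patients, and nP and nN the true POLEmut and NSMP numbers. Suppose there is no true subtype difference, the mix is the same in every subtype, and untested POLEmut is counted as NSMP. Then:

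- observed POLEmut rate = tested rate
- apparent POLEmut − NSMP difference = g·v·(nN + nP) / (nN + v·nP)

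Example with g = 8 points and v = 0.5:

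- 232:232 gives 8 × 0.5 × 464 / 348 = 5.3 points
- 70:487 gives 8 × 0.5 × 557 / 522 = 4.3 points

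The documents give neither v, the node rates nor the shares, so all are assumed. The unequal shares are POLEmut 7.5%, NSMP 52.5%, MMRd 25% and p53abn 15% of 928. Rejection rates are for the four-group chi-square test at nominal 5%, from 100,000 simulated tables per case; with nobody untested the test rejects in about 5%.

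| Untested v tested node rate | Untested | Gap, equal groups | Rejects | Gap, unequal shares | Rejects |
|---|---|---|---|---|---|
| 2% v 10% | 30% | 3.7 | about 20% | 2.6 | about 10% |
| 2% v 10% | 50% | 5.3 | about 40% | 4.3 | about 16% |
| 2% v 6% | 30% | 1.8 | about 11% | 1.3 | about 8% |
| 2% v 6% | 50% | 2.7 | about 18% | 2.1 | about 11% |

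If g = 0 there is no false gap.

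**Route 2: left out.** Let u be the share left out (assumed).

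- *Untested patients resemble tested ones, equal loss in each group.* Power = Φ((1.960 + 1.282)·√(1−u) − 1.960), which gives 83 / 77 / 63% at u = 20 / 30 / 50%. The four-group test (3 df, noncentrality 14.17 × (1−u)) gives 82 / 76 / 60%.
- *The 10% allowance is inside 1,032 and missing POLE is the only loss.* Replacing (1−u) by (1−u)/0.9 gives 86 / 82 / 68%.
- *Node rates differ 1:5 between untested and tested patients.* Start from 2.31% v 6.71%, 464 each. The tested rate is 5p / (u + 5(1−u)). At u = 50%, 232 remain in each group. If the ratio between subtypes is constant, the rates become 3.85% v 11.18% and power is about 85%. If the lower rate rises to 3.85% and the gap stays at 4.4 points, the rates are 3.85% v 8.25% and power is about 51%. At 20 / 30% the two cases give about 89 / 88% and 79 / 71%.

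**The case against.** **The cited guidelines may say how to classify without POLE.** Section 6 treats omission as conforming to them. It would therefore be too strong to say that these patients cannot be placed; the protocol states no rule. Placing them by the remaining markers is, however, the route that produces the bias.

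**The 10% allowance may cover them.** Chart review of completed surgery has little ordinary dropout, so this is possible. Section 5 does not say so, and at 20% or more untested the power is still below 90% when untested patients resemble tested ones.

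**The logistic model could adjust.** It could, but no covariates are named. Adjustment also cannot recover POLE status in a stratum where nobody was tested.

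**The sizes are all assumed.** This stands. The untested share, node rates and subgroup shares are not in the documents, and the false gap vanishes if tested and untested patients have equal rates.

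A reader might go further in three ways that the documents do not support.

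- *Power falls to 83 / 77 / 63%.* That series requires untested patients to resemble tested ones, which sits badly with omission being tied to risk and grade. At 50% left out, a 1:5 rate difference alone gives 51–85%. Uneven loss across groups would change it again.
- *Enrolling 1,032/(1−u) restores 90%.* With the same 1:5 rates, keeping 464 tested per group at 20 / 30 / 50% untested gives about 87 / 85 / 80% (constant gap) or 94 / 96 / 99% (constant ratio).
- *The stated 90% is miscalculated.* Its inputs are not given, so no arithmetic error is shown.

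**Conclusion.** The concern holds as a missing classification rule that affects the primary comparison. Sections 6 and 7 do not fit together: one admits patients without a POLE result, and the other has no place for them.

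If they are placed by other markers, the POLEmut and NSMP rates can differ for reasons that are not molecular. Under the assumptions shown, the false gap is about 1.3–5.3 points, a range that includes the 4.4-point design difference, and the test rejects in about 8–40% instead of 5%. This depends on node rates differing between tested and untested patients, which is plausible because omission follows risk and grade but is not documented.

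If they are left out, the stated 90% is not assured. The loss could be small or large, and no single figure can be defended from the documents.

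**What to change.** 1. **Section 7.** Record whether POLE was tested, add a category for POLE not tested, and keep these patients out of groups 1–4 in the primary analysis.
2. **Section 8.** Report each subtype's node rate with an exact 95% confidence interval by risk group. Compare subtypes within risk group, or put risk group and grade in the planned logistic model. Define risk group here without the molecular result, because section 3 notes that ESGO has built the molecular classification into its risk groups. Where POLE was not tested in a risk group, say that the POLEmut and NSMP rates cannot be estimated there.
3. **Sensitivity analysis.** Place untested patients by their other markers and show how far the rates move.
4. **Section 5.** State that the 90% refers to patients with a complete molecular classification, and restate the power for the number actually classifiable. Do not rely on a total scaled up by the untested share.

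The rule should be fixed before results by subgroup are seen.

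**Cost.** One database field, one category and one extra analysis, with no new tests and no patient contact. The price is precision and a shift in population. Rates will be less precise, and the overall MMRd and NSMP rates, as well as POLEmut, will move towards tested, higher-risk patients. With 2% v 10%, an overall rate of 0.3 × 2 + 0.7 × 10 = 7.6% (30% untested) or 0.5 × 2 + 0.5 × 10 = 6% (50% untested) becomes 10%. That is why the rates must be shown by risk group.
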